9 TREATMENT/INTERVENTION PLAN

- 9.1 Phase I
- 9.1.1 General Outline

During phase I approximately 0.5 ml of the first Bs-Ab infusion will be collected about half-way through the infusion and assayed in Neuroblastoma research laboratory to determine quantity of hu3F8-BsAb in the final infusion product. In cycle 1, blood is drawn for PK studies as described in Section 9.1.4. Patients are admitted for dose 1 of cycle 1 of treatment and will be inpatient for approximately 4 days (minimum 48 hours) though the duration of stay may change if clinically indicated. Subsequent doses can be administered inpatient or outpatient. Patients are monitored for DLT clinically with physical examination, CBC and complete chemistry until Day 28. Patients with DLT will come off treatment HAHA titer is measured after each cycle. HAHA draws require about 5mL of serum. If HAHA develops, cycles are deferred for up to 4 months until HAHA titer until <1300 U/ml. Extent of disease evaluation will be performed after the second dose of hu3F8-BsAb in cycle 2 and cycle 4, every 3 months thereafter. (Table 6) A total of 4 cycles will be given.

Patients with no life-threatening toxicity clearly attributable to hu3F8-BsAb, no PD, and continuing to meet all eligibility criteria (with subsequently explained exceptions) have the option of receiving additional cycles up to 2 years from the start of the hu3F8-BsAb treatment. Inclusion criteria that no longer apply for patients to receive subsequent cycles are: disease status, since patients achieving remission may continue; and prior T cell immunotherapy timing restrictions, since all patients will have received Cycle 1 of hu3F8-BsAb. Even patients who achieve remission may continue therapy beyond

4 cycles. DLT and dose-schedule are described in Section 9.1.2 and 9.1.3. After cycle 2, intra-patient dose escalation will be permitted i.e. patients can receive the highest dose that has been evaluated and proven safe by DLT assessment. Patients will be admitted for at least 48 hours for their first escalated dose.

The treatment and evaluation schedule may require minor adjustment as clinically indicated or due to circumstance (e.g. due to PDH closure for holidays or due to inclement weather).

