
unlikely event that patient stops the drug due to HAHA before completing the first cycle, this patient will be considered inevaluable and will be replaced. If life-threatening toxicity occurs in any patient, further accrual at that dosage will be stopped pending review by the Principal Investigator (PI) or Co-PI. Toxicity at each dosage level is evaluated during the 28 days following the first dose of hu3F8-BsAb. No more than two patients will receive their first dose of hu3F8-BsAb within a 24 hour period. If no DLT is observed up to dose level 12 during the initial patient per dose escalation (e.g. no MTD), the RP2D will be determined as a minimum dose that gives the highest hu3F8-BsAb serum levels based on the PK data.

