9.1.2.2 Dose Limiting Toxicities

Toxicity will be monitored using CTCAE version 4.0. DLT only during cycle 1, i.e. Days 1 through 28. Allowance will be made for the expected toxicities of hu3F8 from which hu3F8-BsAb was derived. (See Section 11.2). As stated above, in the first stage (1 patient per dose-level) dose-escalation will be performed until \geq Grade 2 related toxicity (except for Grade 2 sinus bradycardia, sinus tachycardia, urticaria, fever, nausea, vomiting, diarrhea, urticaria, headache, paresthesia, electrolyte disturbances, pain) is encountered, then the subsequent dose allocation will follow the CRM.^{75,76}

During the CRM phase, any \geq Grade 3 toxicity attributable to hu3F8-BsAb will be considered doselimiting with the following exceptions:

- Grade 3 cytokine release syndrome (CRS) improving to ≤Grade 1 CRS within ≤72 hours after starting systemic steroids (See Section 11.3 for a grading system and algorithm)
- Grade 3 pain improving to \leq Grade 2 within \leq 72 hours of its onset. Grade 3 pain associated with myalgia is an expected clinical toxicity associated with cytokine release syndrome (CRS).
- Grade 3 neutropenia or anemia
- Grade 3 thrombocytopenia without clinically significant bleeding.
- Grade 4 lymphopenia
- Grade 3 elevations of AST, ALT if they return to <Grade 3 by day 28
- Catheter related infections
- DLT of hypertension is defined as persistent hypertension higher than 99th percentile for >48 hours.

The following Grade 3 toxicities are related to infusion of monoclonal antibodies and will not be considered DLT if they resolve to <Grade 3 within 24 hours:

- Allergic reactions controlled with supportive care measures
- Vasovagal reaction
- Sinus bradycardia

- Sinus tachycardia
- Urticaria (improved to at least Grade 2)
- Fever

The following Grade 3 toxicities will not be considered a DLT if they resolve within 48 hours:

- Nausea
- Vomiting
- Diarrhea
- Peripheral neuropathy (paresthesia)
- Electrolyte disturbances

In all other cases, DLT is defined as Grade 3 or greater toxicities occurring during cycle 1 with the exception of toxicities clearly related to disease activity or co-interventions.

9.1.3 Criteria for continuing on therapy beyond cycle 1.

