10 EVALUATION DURING TREATMENT/INTERVENTION

10.1 History and physical exam

- Phase I cycle 1: History and physical exams will be completed every day for the first 4 days, on Day 8, and weekly thereafter until Day 28.
- For subsequent cycles in Phase I, and Phase II: Before each dose of hu3F8-BsAb and within 72 hours of treatment.
- **10.2** Patients are monitored by pulse oximeter during hu3F8-BsAb infusion and have blood pressure taken no later than 30 minutes after the end of infusion of hu3F8-BsAb. In cycle 1 and for all inpatient treatment, blood pressure measurement (standing, sitting and lying down) will be taken pre infusion, once daily throughout their hospital stay and at discharge. For treatment administered outpatient, blood pressure measurement (standing, sitting and lying down) will be taken pre infusion and at discharge.
- 10.3 CBC
 - Phase I cycle 1: CBC will be done approximately on Days 2, 5, 8 (prior to the second dose of hu3F8-BsAb), and approximately Days 15 and 28.
 - For subsequent cycles in Phase I, and Phase II: Before each dose of hu3F8-BsAb. (Pre-treatment CBC can be used for pre-cycle 1 CBC.)

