10.5 Urinalysis

- Phase I only: In cycle 1, urinalysis will be tested prior to each dose of hu3F8-BsAb and approximately one week after the second dose. (Pre-treatment urinalysis can be used for pre-cycle1 test.)
- **10.6** Liver and kidney function blood tests (ALT, AST, alkaline phosphatase, albumin, bilirubin, BUN and creatinine), and serum electrolytes (sodium, potassium, chloride, bicarbonate, magnesium, and phosphate).

- Phase I cycle 1: Before each dose of hu3F8-BsAb, within 72 hours after each dose of hu3F8-BsAb, and on approximately Day 15. (Pre-treatment test can be used for pre-cycle1 test.)
- For subsequent cycles in Phase I, and Phase II: Before each dose of hu3F8-BsAb. (Pre-treatment test can be used for pre-cycle1 test.)
- **10.7** Pregnancy test within 2 weeks before each cycle, if applicable.
- **10.8** Phase I only: Electrocardiogram will be done post the first infusion of hu3F8-BsAb on Day 1 and prior to the second dose hu3F8-BsAb on Day 8 during cycle 1. This must be done on the same day as the dose, but does not need to be immediately post or immediately prior.
- **10.9** Phase I only: Pharmacokinetic studies will be done as described in Section 9.1.4
- **10.10** Phase I and II: Cmax and Ctrough will be measured as described in Section 9.1.4
- **10.11** Ferritin and C-reactive protein
 - Phase I cycle 1: On Day 8 (prior to the second dose of hu3F8-BsAb) and approximately on Day 28.
 - For subsequent cycles in phase I, and phase II: If CRS is suspected based on clinical symptoms. (See Section 11.3)
- 10.12 LDH
 - Phase I cycle 1: On Day 8 (prior to the second dose of hu3F8-BsAb) and approximately on Day 28.
 - For subsequent cycles in phase I, and phase II: If CRS is suspected based on clinical symptoms. (See Section 11.3)
- **10.13** Blood will be obtained before each cycle of hu3F8-BsAb to assay for HAHA titers, then approximately every 3 months for 24 months from first hu3F8-BsAb dose, and then approximately every 6 months for up to 5 years from first hu3F8 dose or until patient is off study, whichever is earlier. This blood sample may also be tested for HAMA.
- **10.14** Blood will be tested for cytokine studies including IFN-y, IL-6, IL-8, IL-10.
 - Phase I cycle 1: cytokine studies should be tested prior to and ~ 6-8 hrs after the first and second infusion of hu3F8-BsAb, and on Days 2, 3, 4, 9, 10, and 11.
 - For subsequent cycles in Phase I and Phase II: If CRS is suspected based on clinical symptoms. (See Section 11.3)

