- 10.18 Pain Assessment (Phase I only): Pain scores will be assessed using the Face, Legs, Arms, Cry, Consolability (FLACC) scale⁸²⁻⁸⁴ and/or the numeric scale⁸⁵, as appropriate (see Appendix A for pain scales). Pain scores will be evaluated at the following time points on days with hu3F8-BsAb treatment: (a) once prior to commencement of any study drug administration, (b) at least once during the acute pain episode when rescue pain medication doses are required (for hu3F8 this is towards the end of the 30 minute infusion or soon after completion of antibody infusion) and (c) ~1 hour after the end of infusion or prior to discharge from the Pediatric Day Hospital. Pain scores will be used to establish safety for the Phase I primary objective (Section 2.1). Pain scores will be used to assist clinical judgment (e.g. decision of pain medication use, observation of pain relief) and for documentation.
- **10.19** Phase I and II: stool sample collection as described in section 9.6.

All research blood (as identified below) will be completed where feasible. Patients who are 10 kilograms or less in weight will only have research bloods drawn at the discretion of the Principal Investigator.

Tests	Pre- treatment	During Treatment	During Follow-up
Complete history and physical	V	Cycle 1: Daily from Day 1 through Day 4, on Day 8, then weekly thereafter until Day 28 Subsequent Cycles: Before each dose of hu3F8-BsAb and within 72 hours of treatment	-
Pharmacokinetic studies (research blood)	\checkmark	See Section 9.1 Cycle 1: As shown in Table 5 Subsequent Cycles: Before each dose of hu3F8-BsAb, ~5 minutes after hu3F8-BsAb infusion	
Complete blood count	~	Cycle 1: Approximately Days 2, 5, 8 (prior to the second dose of hu3F8- BsAb), and approximately Days 15 and 28. Subsequent Cycles: Before each dose of hu3F8-BsAb	_
Liver and Renal function tests (ALT, AST, alkaline phosphatase, albumin, bilirubin, BUN and creatinine) and serum electrolytes (sodium, potassium, chloride, bicarbonate, magnesium, and phosphate)	~	Cycle 1: Before each dose of hu3F8- BsAb, within 72 hours after each dose of hu3F8-BsAb and approximately Day 15 Subsequent Cycles: Before each dose of hu3F8-BsAb	_
C3 & CH50	\checkmark	Cycle 1 Only: Day 2	-
LDH	\checkmark	Cycle 1: Day 8 and approximately Day 28 Subsequent Cycles: If CRS is suspected based on clinical symptoms	

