2.1.1.5. Dose Limiting Toxicities

Toxicity will be monitored using Common Terminology Criteria for Adverse Events (CTCAE) version 4.0 or later. The DLT period corresponds to days 1 through 28 in cycle 1. Allowance will be made for the expected toxicities of hu3F8 from which hu3F8-BsAb was derived (See Protocol Section 11.2). As stated above, in the first stage (1 patient per dose-level) dose-escalation will be performed until \geq Grade 2 related toxicity (except for Grade 2 sinus bradycardia, sinus tachycardia, urticaria, fever, nausea, vomiting, diarrhea, urticaria, headache, paresthesia, electrolyte disturbances, pain) is encountered, then the subsequent dose allocation will follow the CRM.

During the CRM phase, any \geq Grade 3 toxicity attributable to hu3F8-BsAb will be considered dose-limiting with the following exceptions:

- Grade 3 Cytokine Release Syndrome (CRS) improving to ≤ Grade 1 CRS within ≤ 72 hours after starting systemic steroids (See Protocol Section 11.3 for a grading system and algorithm)
- Grade 3 pain improving to \leq Grade 2 within \leq 72 hours of its onset. Grade 3 pain associated
- with myalgia is an expected clinical toxicity associated with CRS.
- Grade 3 neutropenia or anemia
- Grade 3 thrombocytopenia without clinically significant bleeding.
- Grade 4 lymphopenia
- Grade 3 elevations of Aspartate Aminotransferase (AST), Alanine Aminotransferase (ALT) if they return to < Grade 3 by day 28
- Catheter related infections
- DLT of hypertension is defined as persistent hypertension higher than 99th percentile for > 48 hours.

The following Grade 3 toxicities are related to infusion of monoclonal antibodies and will not be considered DLT if they resolve to < Grade 3 within 24 hours:

- Allergic reactions controlled with supportive care measures
- Vasovagal reaction
- Sinus bradycardia
- Sinus tachycardia
- Urticaria (improved to at least Grade 2)
- Fever

The following Grade 3 toxicities will not be considered a DLT if they resolve within 48 hours:

- Nausea
- Vomiting
- Diarrhea
- Peripheral neuropathy (paresthesia)
- Electrolyte disturbances

In all other cases, DLT is defined as Grade 3 or greater toxicities occurring during cycle 1 with the exception of toxicities clearly related to disease activity or co-interventions.

2.1.1.6. Criteria for Continuing on Therapy beyond Cycle 1

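### Protocol 9.1.1 promises chemistry for DLT monitoring to Day 28 and the AST/ALT exception turns on Day 28, but the detailed schedules list no Cycle 1 chemistry after about Day 15

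*Protocol*

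**What the plan says.** **The window.** Protocol 9.1.2.2 sets it: "DLT only during cycle 1, i.e. Days 1 through 28". Section 9.1.2.1 agrees: "Toxicity at each dosage level is evaluated during the 28 days following the first dose of hu3F8-BsAb".

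**The exception.** Protocol 9.1.2.2 excuses "Grade 3 elevations of AST, ALT if they return to <Grade 3 by day 28". SAP 2.1.1.5 repeats the condition: "if they return to < Grade 3 by day 28". Of the listed exceptions, this is the only one tied to Day 28.

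**The general monitoring statement.** Protocol 9.1.1: "Patients are monitored for DLT clinically with physical examination, CBC and complete chemistry until Day 28". It gives no draw days.

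**The detailed schedules.** Protocol 10.6 lists Phase I Cycle 1 liver, renal and electrolyte tests as "Before each dose of hu3F8-BsAb, within 72 hours after each dose of hu3F8-BsAb, and on approximately Day 15". Protocol Table 6 and SAP Table 2 both end at the same point: "within 72 hours after each dose of hu3F8-BsAb and approximately Day 15".

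**What is drawn later.** Section 10.3 schedules the CBC to run further, with draws before Day 15 "and approximately Days 15 and 28". Sections 10.11 and 10.12 put ferritin, CRP and LDH at about Day 28, and Protocol Table 5 has a PK sample at about Day 28.

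**The concern.** The occurrence of DLT in Cycle 1 is the Phase I primary endpoint (SAP 2.4.1), and it is what the CRM uses to assign the next dose. Transaminitis is a named side effect of the parent antibodies (Protocol 11.2), so a Grade 3 AST/ALT is a foreseeable event. The panel that decides the exception is absent from the draw at about Day 28, although other blood tests are taken then. Staff who follow Table 6 and staff who follow 9.1.1 would collect different data on the same patient.

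Two kinds of patient are affected. One has a Grade 3 AST/ALT at about Day 15, where the verdict depends on a later value that no detailed schedule calls for. The other develops a silent laboratory abnormality after Day 15, when none of these tests is scheduled within the window.

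**Working it through.** **1. Coverage of the DLT window.** Under 10.6 and the two tables, Cycle 1 chemistry falls before the Day 1 dose, within 72 hours after it, before the Day 8 dose, within 72 hours after it, and at about Day 15. Days without a scheduled test after the last one: 28 − 15 = 13, and 13/28 = 46%. This is a share of calendar time, not of DLTs missed. The documents give no rate of late laboratory toxicity.

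**2. The next scheduled chemistry.** It is the test before the first dose of Cycle 2. With 28-day cycles that dose falls on about Day 29. If Cycle 2 is delayed for toxicity, 9.1.3 allows 56 days between first doses, so the dose may fall as late as Day 1 + 56 = Day 57. Nothing requires the sample by Day 28, and it is not taken if Cycle 2 is not given.

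**3. Patients who stop but still count.** Protocol 13.1 takes patients with progression off treatment. Protocol 12.6 keeps a Phase I patient evaluable if progression follows completed Cycle 1 treatment and no other therapy is given before Day 28. SAP 4.5 admits patients who had both doses and enough safety evaluation, without defining enough. Such a patient can enter the CRM as no DLT with no scheduled chemistry after about Day 15. SAP 5.2.2 says that missing laboratory data are in general not imputed.

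**4. What one verdict is worth to the CRM.** Inputs from Protocol 9.1.2.1 and 14.1.1: initial DLT estimates p = 0.001, 0.005, 0.01, 0.025, 0.05, 0.075, 0.10, 0.15, 0.25, 0.35, 0.45, 0.50; exponential prior on a with mean 1; target 0.15; no escalation of more than one level. Because a = 1 returns the initial estimates, the model is P(DLT at level i) = p_i^a.

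Assume one patient at each level below k, none with a DLT, and change the verdict of one patient at level k. With one patient at k, the posterior is proportional to
- no DLT: e^(−a) × Π(i ≤ k) (1 − p_i^a)
- DLT: e^(−a) × p_k^a × Π(i < k) (1 − p_i^a)

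A second patient at k without a DLT multiplies each by (1 − p_k^a). The documents do not say whether the next dose uses p_i raised to the posterior mean of a (plug-in) or the posterior mean of p_i^a, so both are shown.

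| Verdict, patients at k, estimator | k=5 | k=6 | k=7 | k=8 | Difference in levels |
|---|---|---|---|---|---|
| No DLT, one or two, either (after the one-level cap) | 6 | 7 | 8 | 9 | reference |
| DLT, one, plug-in | 4 | 5 | 6 | 7 | 2 |
| DLT, one, posterior-mean probability | 3 | 4 | 5 | 6 | 3 |
| DLT, two, plug-in | 5 | 6 | 7 | 8 | 1 |
| DLT, two, posterior-mean probability | 4 | 4 | 5 | 6 | 2, 3, 3, 3 |

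Example for k = 5, plug-in. With one patient at level 5 and a DLT, the posterior mean of a is 0.530. Then 0.025^0.530 = 0.142 at level 4 and 0.05^0.530 = 0.204 at level 5, so level 4 is nearest 0.15. With two patients and one DLT the mean is 0.590. Then 0.025^0.590 = 0.114 and 0.05^0.590 = 0.171, so level 5 is nearest.

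**The case against.** The best case for the plan is that a reader who sees only Table 6 might infer too much.

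*That the AST/ALT rule cannot be applied.* The documents do not support this. A rise already below Grade 3 by about Day 15 meets the exception on scheduled data. One still present then is a known event, and Protocol 17.3 requires related Grade 3 or higher events to be followed regularly until resolved, chronic or stable. The exception is also conditional on a return, so on a plain reading an undocumented return leaves the event a DLT, which is the cautious default. This stands. But 17.3 leaves the timing to clinical judgment, so it does not guarantee a value by Day 28, and it covers only events already detected.

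*That late laboratory DLTs go unseen.* This is also too strong. Protocol 9.1.1 does promise chemistry to Day 28. Chemistry is scheduled before each later dose, and 9.1.3 requires eligibility to be met again before each cycle, which rules out renal or hepatic toxicity of Grade 3 or more (6.2). Examinations run weekly to Day 28. Patients off treatment for progression are followed for toxicity for 30 days after the last dose, to about Day 38 after a Day 8 dose. This stands for persistent or symptomatic events. None of it calls for a dated blood test before Day 28 in a patient without symptoms.

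*That electrolytes need a separate fix.* The 48-hour electrolyte exception has no timed repeat test either. A known Grade 3 value falls under 17.3 and the same cautious default, and a protocol need not schedule every conditional repeat. No separate request is warranted.

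*That one verdict always moves the dose two or three levels.* The largest shifts need a sparse history or a particular estimator. With two patients at level k, the plug-in shift is one level. Protocol 14.1.1 reports five patients on levels 1 to 4, so not every level has held a single patient.

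**Conclusion.** The point holds as a contradiction between Protocol 9.1.1 and the detailed schedules, and it leaves a partial gap in ascertaining the Phase I primary endpoint. Two consequences follow:

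- A Grade 3 AST/ALT still present at about Day 15 is not guaranteed a value by Day 28.
- An asymptomatic laboratory DLT may be recorded as no DLT if it starts and resolves after about Day 15, or if it arises late in a patient who never starts Cycle 2 but stays evaluable.

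The uncovered time is 13 of 28 days. How often an event falls in it cannot be estimated from the documents. One changed verdict moves the next CRM assignment by one to three levels at k = 5 to 8. That range assumes the initial DLT estimates are used as stated (the plan allows them to be revisited), no earlier DLT, and one or two patients at the current level.

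This should be fixed, but it does not undermine the design: most persistent or known abnormalities would still be found.

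**What to change.** Reconcile Protocol 9.1.1, 9.1.2.2, 10.6 and Table 6 with SAP 2.1.1.5 and SAP Table 2. Add the liver, renal and electrolyte panel to the existing draw at about Day 28 of Cycle 1, for every DLT-evaluable patient and whether or not Cycle 2 follows. The DLT definition itself need not change.

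In SAP 4.5, define the safety evaluation needed for the DLT-evaluable set so that it matches, naming the Day 28 chemistry.

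The cost is one added tube at a draw already planned, plus a schedule edit in the next protocol amendment and the matching SAP text.

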9.1.4 Pharmacokinetic (PK) studies

Blood (Table 5) will be drawn at various time points to study PK of hu3F8-BsAb. At each timepoint about 2 mL of blood will be collected for PK studies. For further details, see the laboratory manual.

Day	Time points		
1	Prior to infusion of hu3F8-BsAb infusion		
1	\sim 5 mins, 3 hrs, \sim 6-8 hrs after the end of hu3F8-BsAb infusion		
2	~24 hrs		
3	~48 hrs		
4	~72 hrs		
5	~96 hrs		
6	~120 hrs		

 Table 5
 PK schedule- Cycle 1 and Dose-Escalated Cycles

Day	Time points		
7	~144 hrs		
8	~168 hrs (prior to hu3F8-BsAb injection) If dose 2 of hu3F8-BsAb cannot be given on Day 8, a PK sample should still be drawn		
8	\sim 5 mins after the end of hu3F8-BsAb infusion dose 2		
9	~24 hrs		
10	~48 hrs		
11	~72 hrs		
12	~96 hrs		
13	~120 hrs		
14	~144 hrs		
15	~168 hrs		
Approximately 22	~336 hrs		
Approximately 28	~480 hrs		

In addition, based on our prior studies demonstrating that Cmax is highly correlative with AUC for hu3F8, patients treated both in phase I and II will undergo a single blood draw \sim 5 minutes after each hu3F8-BsAb infusion for determining Cmax for repeat dosing. We will also draw blood for Ctrough prior to the second dose of hu3F8-BsAb, prior to each hu3F8-BsAb infusion in Phase I and prior to each cycle in Phase II. Each blood draw for Cmax and Ctrough will be about 2ml. Blood for HAHA testing can be used for Ctrough prior to each cycle (see 9.3).

9.1.5 Prohibited medication phase I

No simultaneous systemic anti-cancer therapy is permitted while on study, however local radiotherapy or surgical resection of the tumor is allowed >28 days after first dose of hu3F8-BsAb in phase I provided at least one non-irradiated tumor site is available for evaluation.

